## **10. ETHICAL ASPECTS**

This study will be carried out following the ethical principles recovered in the Declaration of Helsinki from Brazil, October 2013.

This study will be conducted according to Spanish regulations regarding biomedical investigations (Organic Law 14/2007 of biomedical investigation)

The required documentation prior to the start will be:

- Protocol approval by the Ethics Committee.

Confidentiality requirements will follow the required Data Protection legislation (see section 10.3).

### **10.1. Benefit/Risk evaluation**

Participating in this study offers the option of being screened against Hepatitis C Virus, in the context of a full Screening of other STI that are not the objective of this study. Complete assessment and information about transmission ways and possible ways of protection will be offered during the visit.

Participating in this study has not significant risks. Only those associated to capillary blood sampling that can implicate little bleeding or pain in the puncture area.

### **10.2. Patient information and informed consent**

The investigator will inform the candidates of the nature, duration, and purpose of this study and, in addition, of all the inconveniences and obstacles that, if any, can be expected. In addition, written information will be provided to the patient. Patients must have the legal capacity to give their consent and exercise their freedom of decision. Written informed consent will be obtained by signing the study informed consent form.

One copy of the signed IC will be facilitate to the participant.

The consent forms will be reviewed whenever there were changes in the study procedures or new information were available that may affect the patient's willingness to participate. Patients will reconfirm consent with the most recent version of the consent forms during their participation in the study, and the process will be recorded in the medical record by the investigator.

All signed and dated consent forms must remain in the investigator site file and must be available for verification at any time.

### **10.3. Confidentiality**

The processing of the data will be performed in accordance with Spanish Organic Law 3/2018 (LOPD-GDD), which develops the General Data Protection Regulation 2016/679 on data protection and privacy for all individuals within the European Union (GDPR). The individuals and donors will be guaranteed anonymity, and at the time of informed consent signature were informed that all communication shall take place between him/her and the investigator of the study they participated in. This study will be conducted using pseudonymized data. The patient will be identified in the records by the corresponding unique code number, not associated with any of his/her personal data. The database used for this study, is SALUS (Microsoft® SQL Server).

In order to prevent improper access by unauthorized third parties, security measures will be implemented such as the pseudonymisation of the data, the control of access to the database SALUS (Microsoft® SQL Server) through secure personal passwords and its storage on a secure server located in the European union under current regulations with the highest quality and specific security and, if necessary, encrypted data transfer.

The data controller will be the co-sponsors of this project:

- La Fundación FLS de Lucha contra el Sida y las enfermedades infecciosas, ([[contact]](mailto:[contact]))
- PROJECTE DELS NOMS-HISPANOSIDA, [[contact]](mailto:[contact])
- In addition, the data controller of the data that will be integrated in the participant's Medical History will be the *Institut Català de la Salut*, [[contact]](mailto:[contact]).

Data transmitted to third countries, and other countries, will in no case contain personal data. If such transfer occurs, it will be for the same purposes of the study described and ensuring confidentiality, at least to the level of protection of the law in Spain.

## **11. PRACTICAL CONSIDERATIONS**

### **11.1. Study plan**

June 2021-May 2022 Phase 1

June-July 2021 Phase 1 data Analysis and Pre-Test Score development.

August 2022-July 2023 Phase 2

August 2023- January 2024 Phase 2 analysis and results reporting

February 2023-September 2024 6 and 12 months post treatment visits.

October 2024-November 2024- Reinfections reporting

### **11.2. Follow-up and final reports**

It's planned an interim analysis report at 6 and 12 months after the study initiation.

A final report will be performed with the obtained results.

### **11.3. Results diffusion**

It is planned to communicate this study in national and international conferences of socio-sanitary interest and one or many English publications (peer review).

### **11.4. Risks and potential limitations**

As this project will be included in an ongoing project of community screening, recruitment is not expected to be a problem, however intensification of campaigns for promotion of HCV testing will be considered in case of lack of interest in our actual users.

Questions related to risk factors such as number of sexual contacts, drug use, etc. will be asked by the counselor and could produce an underestimation of these risk factors. However, we have been working with this kind of questionnaires for the last 15 years and users have never expressed any problem due to a peer-to-peer service, which allows a safe environment for the clients. All our staff and volunteers are previously selected and adequately trained.

Users with positive results could refuse to attend the medical specialist in the Hospital Germans Trias due to the distance. In this case derivation to other Hospital could be considered. However, treatment will last only 8-12 weeks and usually require no subsequent follow-up. So, in our opinion the interference of this problem in this study would be extremely limited, other Hospitals on the city are working in Test and Treat HCV strategy and referral has been done in the past; also, we will ask for follow up with the participant through telephone calls.

The Partner notification potential Contacts will be performed in our center in collaboration with the Public Health agency to offer testing to positive case contacts. However, in the MSM community this can sometimes be difficult or even not possible because users don't keep in contact with the most part of their sexual partners. From our center we are going to facilitate to get a test in all suspicious cases of contact to other cases.

Our team has been trained during years in the use of rapid tests, including HIV ELISA, PCR, and Syphilis rapid tests. In this cases HCV viral load could be performed at the same time, but also HCV serology could be sent to the lab, as BCN Checkpoint disposes of nurses and doctors at all opening hours (from 8.00 to 20.00 hours) to perform common blood test through standard venipuncture.

Migrants or undocumented population could have difficulties in their access to the required HCV treatment. In case of confirmation of active HCV and no possibilities of treatment, our center has the possibility to facilitate fast access to the Public Health system to facilitate access to care and treatment, as it is considered a Health priority to eradicate HCV by 2030 in the context of WHO's Global Health Sector Strategy on Viral Hepatitis program. This circuit has been used for HIV confirmed cases and the Public Health Agency is aware of this study and this possibility.

### **11.5. Expected Outcome**

It is expected that HCV screening has a good acceptance in the community. It is also expected to be easy to implement both the HCV test and HCV viral load as the center is used to this kind of tests.

According to the 4.7% prevalence in the MSM community estimated by the ECDC for 2018, it is expected to find 305 positive cases of seroprevalence of HCV infection, but it is unknown how many of them will be viremic, as HCV has actively been treated with DAAs in Spain. Therefore, it will be difficult to determine the number of acute HCV infection cases to be found if HCV viral load screening is performed. Also, in our cohort this number might be influenced by the fact that the center attends a migrant community with higher rates of HCV as well as more frequent Chemsex users.

All these facts make it difficult to estimate the potential number of acute HCV cases, but we expect to find 10-15 cases of acute infections.

Implementing HCV screening among the MSM community will increase the detection of acute cases and, due to higher infectiousness, we can contribute to increase the reduction of the transmission chain among the MSM community. Creating a model that could be implemented in other community centers like BCN Checkpoint will increase HCV detection and treatment, working in line with the WHO 2030 objectives of HCV eradication.

It is also expected that acute HCV detections and partner notification create more awareness around MSM about the importance of HCV prevention.

**Appendix 1. Informed Consent**

Attached separately in an independently versioned document.

**Appendix 2. Sexual behaviors and demographics questionnaire**

Attached separately in an independently versioned document.

**Appendix 3. Satisfaction questionnaire PROMs (SUCE Adaptation)**

Cuestionario de Satisfacción del Usuario										
Por favor puntúe de 1 a 10 las siguientes preguntas, siendo el 10 la respuesta mejor valorada y el 1 la respuesta peor valorada										
1. El tiempo que pasó desde que pidió la cita hasta la fecha de consulta	1	2	3	4	5	6	7	8	9	10
2. Los trámites que tuvo que hacer en recepción	1	2	3	4	5	6	7	8	9	10
3. El tiempo de espera hasta ser atendido	1	2	3	4	5	6	7	8	9	10
4. La comodidad de la sala de espera	1	2	3	4	5	6	7	8	9	10
5. El trato por parte del personal	1	2	3	4	5	6	7	8	9	10
6. El cuidado con su intimidad durante la consulta	1	2	3	4	5	6	7	8	9	10
7. La duración de la consulta	1	2	3	4	5	6	7	8	9	10
8. La información clínica recibida	1	2	3	4	5	6	7	8	9	10
10. La claridad con que le explicaron las pruebas realizadas	1	2	3	4	5	6	7	8	9	10
11. La facilidad de los trámites que ha tenido que hacer si ha necesitado volver a citarse	1	2	3	4	5	6	7	8	9	10

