#### Secondary objectives

- Characterization of risk factors associated with acute and chronic HCV infection in the MSM and TGW community to inform which individuals will benefit more from HCV screening.
- Creation of an HCV pre-test Score during Phase 1 and validation during Phase 2.
- Evaluate user's satisfaction with HCV testing using Patient Reported Outcome Measures (PROMs).
- Evaluation of causes for treatment delay and/or loss to follow up.
- Evaluation of reinfections after treatment during first year post treatment.

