## 6. INFORMATION SOURCE AND FIELD

Source documents are the patient's medical records.

Study data will be collected through integrated forms in Salus (QSOFT, Software Salus 2017) that is software to compile user's information used in sites participating in this study. It is allocated in a Secure Server according to Personal Data protection Laws.

During the screening visit, the investigator will provide the participant the informed consent and will let the necessary time to read and understand the study procedures. If the participant agrees to participate in the study, he will sign the consent. One copy of the signed IC will be facilitate to the participant.

A demographics and a sexual behavior questionnaire will be requested to be completed by the study participants at the screening visit (See Appendix 2). Additionally, at the end of each study visit, PROMs questionnaire to evaluate satisfaction will be carried out (See appendix 3)(*In this study and adaptation of SUCE questionnaire will be performedxi*).

Additionally, and in case to be necessary it will be asked to the participant information related to previous HCV infections or in case of a diagnostic to follow treatment received and results of blood test performed on other public health units of Catalonia.

The study visits will be performed in the clinical installations of BCN CheckPoint or BCN PrEP·Point, allocated in Barcelona [name] respectively.

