## 8. VARIABLES AND MEASURE INSTRUMENTS.

### 8.1. Study Variables

- Determination of acute HCV cases detected by viral load.
- Number of positive viremic results and cases per 100 person-years.
- HCV serologic prevalence.
- Number of positive serologic test with or without positive viremia.
- Time between confirmed diagnostic and start of treatment (Measured in days).
- Number of reinfections at 6 and 12 months after treatment.
- Identification of risk factors using the sexual behavior and demographics questionnaire
- Ratio of satisfaction using "Patient Reported Outcome Measures" (PROMs)
- Causes of treatment delay or loss to follow up
- Reinfections/treatments measured in percentage.

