#### Secondary End-points

- Characterization of risk factors associated with acute and chronic HCV infection in the MSM and TGW community to inform which individuals will benefit more from HCV screening.
- Evaluation of causes for treatment delay and/or loss to follow up a long the study
- Evaluation of reinfections after treatment during first year post treatment.
- Service user's punctuations achieved after experience in HCV testing.

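### The satisfaction form is a generic visit questionnaire, so its scores cannot be attributed to HCV testing, which is what the secondary objective asks about

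*Combined protocol and SAP*

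**What the plan says.** The secondary objective (section 5.2) reads "Evaluate user's satisfaction with HCV testing using Patient Reported Outcome Measures (PROMs"). The matching secondary end-point (section 8.2) is worded differently: "Service user's punctuations achieved after experience in HCV testing". The list of study variables (section 8.1) calls the same quantity a ratio of satisfaction, without giving a numerator, denominator or cut-off. Section 9 plans only descriptive reporting of the PROMs.

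On timing, section 6 says that "at the end of each study visit, PROMs questionnaire to evaluate satisfaction will be carried out". Tables 1 and 2 place the form at screening and at the 6- and 12-month post-treatment visits. Section 10.1 describes HCV screening as taking place "in the context of a full Screening of other STI that are not the objective of this study".

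The instrument is an adaptation of an existing questionnaire (SUCE), whose bibliography entry describes it as written for hospital outpatient clinics. Appendix 3 prints ten items in Spanish, numbered 1 to 8, 10 and 11. Item 2, on reception formalities, is typical: "Los trámites que tuvo que hacer en recepción".

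**The concern.** The objective names HCV testing as the thing to be rated, but the form rates the attendance. A participant who comes for a full STI screen gives one score for waiting, one for privacy and one for how the tests were explained. Nothing in those answers separates the HCV component from everything else done that day.

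What is at stake is how the result is read. The protocol's hypothesis is a low-barrier point-of-care HCV model (section 5.1), it expects good acceptance of HCV screening (section 11.5), and the final report is to propose how the model could be replicated elsewhere (section 7.2, Phase 2). If good scores from this form are reported as satisfaction with HCV testing, readers will take them as evidence on the HCV test when they mainly describe the centre.

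**Working it through.** The plan gives no numerical target for satisfaction, so there is no figure to reproduce. The check compares the printed items with the objective, and then asks how many forms come from visits where HCV is the only scheduled test.

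**Step 1. Classify the printed items (Appendix 3).**

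| Topic | Items | Count |
|---|---|---|
| Logistics: time to appointment, reception, wait to be seen, waiting-room comfort, re-booking | 1, 2, 3, 4, 11 | 5 |
| Staff manner, privacy, length of consultation | 5, 6, 7 | 3 |
| Clinical information; clarity of explanation of the tests performed | 8, 10 | 2 |
| Total printed | | 5 + 3 + 2 = 10 |
| Names HCV, the rapid antibody test, the fingerstick viral load, the wait for a result or the fast-track circuit | none | 0 |

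No printed item asks for overall satisfaction either. Number 9 is absent from the print. This may be a numbering gap or a loss in reading the file, so the count covers only the ten items shown.

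**Step 2. Can items 8 and 10 stand in for HCV testing at screening?** They include the HCV test but do not isolate it. Under section 10.1 the visit is a full STI screen, so item 10 covers every test done and item 8 all clinical information given.

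**Step 3. Is the wait for the HCV result covered?** Section 7.2 gives 5 minutes for the antibody result and about 60 minutes for the fingerstick viral load. Item 3 asks about waiting until being seen, which is a different interval. The viral load is planned for 1,000 antibody-negative people in Phase 1 and about 300 people in Phase 2, that is 1,000 + 300 = 1,300, plus those with positive serology. Most respondents would therefore be rating an attendance with only the 5-minute test, and the form does not tell the two groups apart.

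**Step 4. How much could the post-treatment visits contribute?** In Tables 1 and 2 the only test at these visits is the HCV fingerstick, so there item 10 does refer to HCV testing as far as the study schedule goes. The visits are optional and limited to people diagnosed and treated.

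- Enrolment (section 1.10): 6,000 + 2,000 = 8,000 to 7,000 + 3,000 = 10,000.
- Infections expected to be diagnosed and treated (section 5.2): 10 to 15.
- Share of participants: 10 / 10,000 = 0.10% to 15 / 8,000 = 0.19%.
- Forms: at most 15 × 2 = 30 post-treatment forms, against 8,000 to 10,000 screening forms.

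Section 11.5 says the number of viremic cases is unknown. As an extreme bound for Phase 1, suppose that all 305 seropositive cases expected there (4.7% of 6,500 = 305.5) were viremic and treated. The share would still be only 4.7%.

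**Step 5. Does the analysis repair the mismatch?** Section 9 defines no score, item subset or threshold, and the ratio in section 8.1 is undefined. Nothing in the plan picks out an HCV-related part of the form.

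**The case against.** The strongest defence is that the form does produce what section 8.2 literally asks for. The end-point is "punctuations achieved after experience in HCV testing", and a 1-to-10 form completed at the end of a visit that included an HCV test yields scores given after that experience. A reader might infer that the instrument cannot deliver the endpoint at all; the documents do not support that. The mismatch is with the objective in section 5.2, and it is one of content validity and attribution. This part of the defence stands.

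Several further points also stand:

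- The form is not only about appointments, reception and the waiting room. Half of the printed items are on other matters, and items 8 and 10 partly cover HCV testing.
- A reader might infer that a high score would say nothing about the HCV model. That goes too far. The model is low-barrier testing in a community centre, so waiting, privacy, staff manner and clear explanation belong to what would be replicated. The protocol does not make the replication proposal depend on PROM scores.
- A reader might assign each item a tenth of a total score. The plan defines no total, and item-by-item reporting would fit section 9 equally well.
- The fast-track circuit is assessed elsewhere, through days from diagnosis to treatment and causes of delay (section 8.2).
- Adapting an existing questionnaire is a legitimate choice, and rewording the objective would remove the mismatch at almost no cost.

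What the defence does not answer is attribution. At screening, where nearly all forms are collected, no printed item separates the HCV test from the rest of the visit.

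**Conclusion.** The point holds as a limited one. None of the ten printed items isolates HCV testing. The screening scores therefore measure satisfaction with the visit and cannot be attributed to HCV testing, as the secondary objective requires. The post-treatment visits do not change this, because they involve few people: about 0.1% to 0.2% of participants on the protocol's own expectation.

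The conclusion assumes that the ten items shown are the working form; any item 9 cannot be judged. It also assumes that screening attendances usually include other STI tests, as section 10.1 describes.

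Severity is minor. One descriptive secondary endpoint is affected, no test, threshold or decision is attached to it, and no primary endpoint is touched.

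**What to change.** Keep the existing items unchanged and add a few to Appendix 3 on the same 1-to-10 scale:

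1. the HCV finger-prick test;
2. the wait for the HCV result;
3. the explanation of the HCV result;
4. willingness to repeat the HCV test;
5. for viremic participants only, the fast-track circuit, asked once the referral has taken place.

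Report the new items separately as satisfaction with HCV testing, and split them by whether the respondent had the antibody test alone or also the viral load. Report the existing items as satisfaction with the visit. In section 9, state how both sets are summarised, and either define the ratio in section 8.1 or drop it.

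If data are already collected or items cannot be added, reword the objective (section 5.2) and end-point (section 8.2) as satisfaction with the visit that includes HCV testing.

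The cost is a questionnaire amendment and a slightly longer form (four more items for most participants, five for viremic ones) across up to 10,000 people. The added items would not be validated, so they should not be merged with the existing ones into one score. The rewording alternative costs almost nothing, but it gives up any statement about HCV testing itself.

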### **1.11. Calendar**

- Ethics Committee application: June 2021
- Study starts (first patient in): June 2021
- Recruitment period: 2 years and 2 months.
- Patient follow-up: Single visit. Screening. In case of positive HCV viremia, 6 and 12 months post treatment control will be offered.
- Final report: 2023. Reinfections will be reported during 2024.

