**Table 1. Study Chronogram Phase 1**

	SCREENING	6 months Post Treatment visit*	12 months Post Treatment visit*
Informed consent	X		
Selection Criteria	X		
SD BIOLINE HCV assay	X		
Cepheid "Xpert® HCV VL Fingerstick"	a X	a X	a X
Xpert® HCV Viral Load	b X		
Routine Serology	c X		
genotype study/Hematology and biochemical analysis	d X		
Sexual behavior & demographics questionnaire	X		
PROMS questionnaire	X	X	X

- a) The participants that obtain a positive result from the SD Bioline HCV assay test will be confirmed with Cepheid "Xpert® HCV VL Fingerstick" to identify HCV viremic cases. Also first 1000 participants with a negative result from the SD Bioline HCV assay test that fulfills criteria mentioned on 1B point, will be confirmed with Cepheid "Xpert® HCV VL Fingerstick" to identify acute HCV infections. \*During V6MPTV and V12MPTM the fingerstick will be offered to all the participants with HCV infection detected during the screening visit.
- b) Acute infections with negative antibodies will be also tested with (Cepheid "Xpert® HCV Viral Load) to confirm viremic cases.
- c) In case of positive serology with negative viral load, standard lab serology will be performed to confirm serology, through standard hospital lab circuit.
- d) For the confirmed HCV Viremic cases, it will be analyzed the following parameters: blood count, Serum Creatinine, AST, ALT, GGT, alkaline phosphatases, direct and indirect Bilirubin, prothrombin time and the genotype study will be performed.

*\* Visits after 6 months and 12 months are optional and only are applicable for those patients that had been diagnosed and treated for HCV infection during the screening visit.*

After one year, a statistical analysis (interim analysis at 6 months\*) of the results will be made to determine associated factors for positive antibody test as well as for positive acute HCV test to set selection criteria for phase 2 of the study. A Draft of HCV pre-test Score will be developed with this first-year analysis and implemented during second phase.

\*Interim analysis will be used to evaluate data collection, correct incidences and to set up data analysis system. This will facilitate the results evaluation at the end of Phase 1 and it will allow to create the pre-test score to start the study Phase 2.

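### Satisfaction item 11 applies only to users who needed another appointment, but it has no not-applicable option and goes to all participants at screening

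*Combined protocol and SAP*

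**What the plan says.** Appendix 3 prints ten items. Its instruction is "Por favor puntúe de 1 a 10 las siguientes preguntas, siendo el 10 la respuesta mejor valorada y el 1 la respuesta peor valorada", and every row carries the numbers 1 to 10 and nothing else. Item 11 is the only conditional one: "La facilidad de los trámites que ha tenido que hacer si ha necesitado volver a citarse".

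Section 6 sets the timing: "at the end of each study visit, PROMs questionnaire to evaluate satisfaction will be carried out". Tables 1 and 2 in section 7.2 accordingly mark the questionnaire at screening and at the 6- and 12-month post-treatment visits.

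Section 1.11 describes the visit pattern: "Patient follow-up: Single visit. Screening. In case of positive HCV viremia, 6 and 12 months post treatment control will be offered". The footnote to Table 1 narrows this further: "Visits after 6 months and 12 months are optional and only are applicable for those patients that had been diagnosed and treated for HCV infection". Table 2 has the same restriction.

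Satisfaction is a secondary objective (section 5.2) and a secondary endpoint (section 8.2), worded "Service user's punctuations achieved after experience in HCV testing". Section 8.1 lists it as a variable beginning "Ratio of satisfaction using" and then naming the patient-reported measures, with no formula. Section 9 plans a descriptive analysis only. No section defines a total or mean score, or says how a blank or inapplicable answer is treated.

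**The concern.** A conditional question needs somewhere to record that the condition was not met. Item 11 has none. A user who did not re-book can leave the row blank or circle a number that rates nothing. The form has no separate question on whether a re-booking happened, so a circled number from such a user looks exactly like a genuine rating. A blank could equally mean that the item did not apply or that it was skipped.

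This cannot be put right at analysis, because the distinguishing information is never collected. At stake are the item 11 result itself and any overall satisfaction figure that includes it. No test result, case count, risk score or primary endpoint depends on it.

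**Working it through.** **Inputs from the protocol**
- Phase 1 size: 6,000-7,000 (section 1.10). Both phases together: up to 7,000 + 3,000 = 10,000 (section 7.3).
- Infections expected to be diagnosed and treated during the study: 10-15 (section 5.2).
- Expected seropositives: 305, from a prevalence of 4.7%, with the viremic share stated to be unknown (section 11.5).
- Items printed: ten (Appendix 3; the numbering has no item 9).

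**Step 1. Reproduce the plan's figure.** 0.047 × 6,500 = 305.5, which matches 305 at the midpoint of the Phase 1 range. At 6,000 the product is 282, and at 7,000 it is 329.

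**Step 2. Share with a single study visit.** Share = 1 − (cases offered later visits) / N.

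| Cases offered later visits | N | Single study visit |
|---|---|---|
| 15 | 6,000 | 99.75% |
| 10 | 6,000 | 99.83% |
| 15 | 10,000 | 99.85% |
| 10 | 10,000 | 99.90% |
| 305 (all seropositives viremic) | 6,000 | 94.9% |
| 305 | 6,500 | 95.3% |
| 305 | 7,000 | 95.6% |

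The 305 rows are an extreme case and relate to Phase 1, the only phase for which the plan gives a seropositive count. Section 11.5 also applies the range 10-15 to acute infections alone, so the true number of treated cases could lie above 15. That is why the lower bound is shown.

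These shares count study visits. They are not shares of users with no re-booking of any kind, for which the documents give no figure.

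**Step 3. Effect on an overall score, if one were formed.** The plan defines no score, so the scoring rules below are assumptions.
- *Mean of ten items.* Let the other nine items average m and let item 11 be answered x. The mean is (9m + x) / 10, which differs from m by (x − m) / 10. Between x = 1 and x = 10 the mean moves by (10 − 1) / 10 = 0.9 points, the most that an arbitrary answer can do. With m = 8 the mean runs from (72 + 1) / 10 = 7.3 to (72 + 10) / 10 = 8.2. With m = 9 it runs from 8.2 to 9.1.
- *Unadjusted sum out of 100.* With all items at 8, a blank item 11 lowers the total from 80 to 72. With all items at 9, it lowers the total from 90 to 81. This arises only if a blank is counted as zero.
- *Complete forms only.* Everyone who rightly leaves item 11 blank is excluded.
- *Item by item.* Nine of the ten items are unaffected. Only the item 11 result mixes real and inapplicable answers.

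**The case against.** A reader might infer that nearly every participant is made to give a meaningless answer, so that the satisfaction score as a whole is arbitrary or incomplete. The documents do not support that, for four reasons.

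- No composite score is defined. If the descriptive analysis in section 9 goes item by item, only item 11 suffers.
- Nothing makes an answer compulsory. The item carries its own condition, and a user who did not re-book may well leave it blank. How many would circle a number anyway is unknown.
- One study visit does not mean nothing to rate. The item is not limited to study visits. Section 1.10 includes clients already under regular control at the centre, section 7.2 mentions routine PrEP controls, and section 10.1 places the study within a full STI screen. Such clients may have re-booked.
- No comparison of satisfaction between screening and the post-treatment visits is planned, so a bias in that contrast cannot be charged to the plan.

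The form is also an adaptation of a published questionnaire whose scoring conventions cannot be seen here.

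All of this limits the size of the problem. It does not remove it. Clients who did re-book elsewhere at the centre cannot be separated from those who did not, because the form does not ask. The undefined ratio in section 8.1 leaves open an overall figure that includes item 11, and no rule says what to do with blanks.

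**Conclusion.** The point holds in a limited form. Item 11, and any summary that includes it, will mix applicable ratings with inapplicable or missing ones to an extent that the collected data cannot reveal. The population in which this can occur is large: about 95% of Phase 1 participants have a single study visit on the extreme assumption about viremia, and over 99.7% of participants do on the protocol's expectation of 10-15 treated infections. An unknown part of them will have re-booked for other services and so have something to rate.

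The bound of 0.9 points per person rests on an assumed ten-item mean, and the figures for a sum rest on counting a blank as zero. Both are illustrations of possible scoring rules, not predictions. Because the endpoint is secondary and descriptive, the severity is minor.

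**What to change.** Add a *no aplica* box to item 11 in Appendix 3. In section 9, state that item 11 is reported only among users to whom it applies, with their number, and that any overall satisfaction score is the mean of the applicable items answered. If the ratio in section 8.1 is meant to be such a score, define it there in the same terms.

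The cost is one answer box and a sentence or two of text. The downside is that the form departs slightly further from the questionnaire it adapts.
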